**ABSOLUTE BIOAVAILABILITY/PHARMACOKINETIC AND RESIDUAL DRUG ANALYSIS
OF THE TRANSDERM SCOP® SYSTEM IN HEALTHY ADULTS**

Short title: Scopolamine Release from Transdermal Patches in Healthy Adults

Principal Investigator:

[name] (contact), PharmD, PhD

Medically Accountable Investigator:

[name]

Principal investigator contact:

[name], PhD

Assistant Professor, Department of Pharmaceutical Sciences and Experimental Therapeutics

University of Iowa College of Pharmacy

[name]

[name]

[contact]

[contact]

Email: [contact]

09 December 2016

Study title:	Absolute Bioavailability/Pharmacokinetic and Residual Drug Analysis of the Transderm Scōp® System in Healthy Adults
Principal Investigator	[name], PhD
Population:	Healthy, non-smoking adults age 18-65 years
Number of Sites:	Single site: University of Iowa College of Pharmacy/ University of Iowa Clinical Research Unit
Study Duration:	Approximately up to 12 months
Subject Participation Duration:	Approximately 5 – 7 weeks, including the screening period

Description of Study Design

This will be a two arm, open-label, crossover, two treatment sessions study (n=24 healthy adult subjects) with one week washout period between each study session. The two study sessions include an intravenous administration of scopolamine hydrobromide and a transdermal administration of a single strength of the reference listed drug (RLD) Transderm Scōp® patch. Each subject will be his/her own control.

Study products

- Transderm Scōp® patch containing scopolamine (1.5 mg) to be worn for 3 days (72 hr)
- Single intravenous (0.4 mg) administration of scopolamine hydrobromide (0.4 mg/mL)

Study enrollment

Only adult subjects who meet the inclusion/exclusion criteria will be eligible for enrollment into the study. Twenty-four subjects will be recruited, and ten alternates who could replace subjects who drop out from the study for any unforeseen reason. The study population selected for this study includes healthy adult men and women ages 18 to 65, inclusive. Enrollment will continue until 24 complete the study. The selection criteria are designed to exclude persons who might have medical conditions that could pose a safety risk and persons whose medical conditions might interfere with objectives and results of the study.

Inclusion Criteria

Subjects are eligible for this study if they fulfill the inclusion criteria specified below:

1. Men or non-pregnant women of any ethnic background between the age of 18 and 65 years old.
2. Subjects must be non-smokers (must have refrained from the use of nicotine-containing substances, including tobacco products (e.g., cigarettes, cigars, chewing tobacco, gum, patch or electronic cigarettes) over the previous 12 months and are not currently using tobacco products).
3. Provide written informed consent before initiation of any study procedures.
4. Available for follow-up for the planned duration of the study.
5. Able to communicate well with the investigators.
6. Able to adhere to the study protocol schedule, study restrictions and examination schedule.
7. Subjects who are within their ideal body weight (BMI between 18-29.9 kg/m²).
8. Demonstrate comprehension of the protocol procedures and knowledge of study, as demonstrated a study member filling out a consent checklist form to verify that the subject understands all aspects of the study including the purpose, procedures, risks and benefits.

9. Subjects deemed to be healthy as judged by the Medically Accountable Investigator (MAI) and determined by medical history, physical examination, and medication history.
10. Negative urine drug screening test.
11. Have a normal blood pressure (systolic: 90-140 mmHg; diastolic: 50-90 mmHg) and heart rate (55-100 bpm).
12. Have normal screening laboratories for WBC, Hgb, Hct, platelets, sodium, potassium, chloride, bicarbonate, BUN, creatinine, ALT, AST, and total bilirubin.
13. Have normal screening laboratories for urine protein and urine glucose.
14. Female subjects must be of non-childbearing potential (defined as surgically sterile [i.e. history of hysterectomy or tubal ligation] or postmenopausal for more than 1 year [no bleeding for 12 consecutive months]), or if of childbearing potential must be non-pregnant at the time of enrollment and on the morning of the first day of each study treatment session, and must agree to use hormonal or barrier birth control such as implants, injectables, combined oral contraceptives, some intrauterine devices (IUDs), sexual abstinence, or a vasectomized partner.
15. Agrees not to participate in another clinical study during the study period unless the study is in the follow up phase and it has been 1 month since the subject received any experimental agents or treatments. The subject also agrees not to participate in an investigational drug study for at least 1 month after last procedure day.
16. Agrees not to donate blood to a blood bank throughout participation in the study and for at least 2 months after last procedure day.
17. Have a normal ECG; must not have the following to be acceptable: pathologic Q wave abnormalities, significant ST-T wave changes, left ventricular hypertrophy, right bundle branch block, left bundle branch block (sinus rhythm is between 55–100 beats per minute).

Exclusion Criteria

Subjects will be excluded for any of the following conditions/reasons:

1. Women who are pregnant or lactating or have a positive serum pregnancy test at enrollment or positive urine pregnancy test on the morning of the first day of any procedure session.
2. Smokers (current use or use over the previous 12 months of nicotine-containing substances, including tobacco products (e.g., cigarettes, cigars, chewing tobacco, gum, patch or electronic cigarettes)).
3. Participation in any ongoing investigational drug trial or clinical drug trial period unless the study is in the follow up phase and it has been ≥ 1 month since the subject received any experimental agents or treatments..
4. Abnormal vital signs, defined as:
 - Hypertension (systolic blood pressure >140 mmHg or diastolic blood pressure >90 mmHg) at rest on 2 separate days.
 - Heart rate <55 at rest on 2 separate days
 - Respiratory rate ≤ 11 to ≥ 18 breaths per minute
5. Temperature $>38.0^{\circ}\text{C}$ (100.4°F) or symptoms of an acute self-limited illness such as an upper respiratory infection or gastroenteritis within 7 days of application of the scopolamine TDDS.
6. History of chronic obstructive pulmonary disease.
7. Positive urine drug screening test.
8. Use of any prescription medication during the period 0 to 30 days or over-the counter medication during the period 0 to 3 days before entry to the study (vitamins, herbal supplements and birth control medications not included).
9. Use of medications or treatments that would significantly influence or exaggerate responses to the test product or that would alter inflammatory or immune response to the product (e.g. antihistamines [within 72 hours prior to dosing], systemic or topical corticosteroids [within 3 weeks prior to dosing], cyclosporine, tacrolimus, cytotoxic drugs, immune globulin, Bacillus Calmette-Guerin [BCG], monoclonal antibodies, radiation therapy).

10. Donation or loss of greater than one pint of blood within 60 days of entry to the study.
11. Any prior serious adverse reaction or hypersensitivity to scopolamine, or any of the inactive ingredients in the patch (light mineral oil, polyisobutylene, polypropylene and aluminized polyester film).
12. Have a diagnosis of schizophrenia or other major psychiatric diagnosis.
13. Received an experimental agent (vaccine, drug, biologic, device, blood product or medication) within 1 month before enrollment in this study or expects to receive an experimental agent during the study.
14. Medical history of a serious chronic condition, including (but not limited to): allergic conditions such as anaphylaxis, asthma or generalized drug reactions; any seizure disorder; glaucoma (open or closed angle); history of pyloric or urinary bladder neck obstruction; intestinal obstruction; difficulty swallowing; stomach or bowel problems (e.g. blockage, muscle weakness, ulcerative colitis, Crohn's disease); bleeding disorders; acid reflux disease; myasthenia gravis; allergy to belladonna alkaloids; impaired hepatic or renal function.
15. Any condition that would, in the opinion of the MAI, place the subject at an unacceptable risk of injury or render the subject unable to meet the requirements of the protocol.
16. Inability to communicate or co-operate with the investigators.
17. Medical history of significant dermatologic diseases or conditions, such as atopy, psoriasis, vitiligo or conditions known to alter skin appearance or physiologic response (e.g. diabetes, porphyria).
18. History of significant dermatologic cancers (e.g. melanoma, squamous cell carcinoma), except basal cell carcinomas that were superficial and did not involve the investigative site.
19. History of consumption of alcohol within 24 hours prior to dose administration.
20. Subject has an obvious difference in skin color between arms or the presence of a skin condition, excessive hair at the application site, sunburn, raised moles and scars, open sores at application site, scar tissue, tattoo, or coloration that would interfere with placement of test articles, skin assessment, or reactions to drug.
21. Use of monoamine oxidase inhibitors 21 days prior to study.
22. Within 4 weeks prior to dosing, use of medications or treatments that would significantly influence or exaggerate responses to the test product or that would alter inflammatory or immune response to the product or agents deemed to be immunosuppressive as determined by physician investigator.
23. Planned MRI scan of the head during TDDS wear.

Study schedule

For the treatments, either the patch will be applied behind the ear or the drug will be intravenously administered. Blood samples will be obtained as follows (based on administration route):

- 60 min pre-application and then up to 120 hr (5 days), during 3 day wear and 2 day post patch removal
- 60 min pre-IV administration and then up to 48 hr (2 days) post start of IV administration

Residual drug analysis determination of strength

In conjunction with the above described study, residual drug analysis will also be conducted for the worn patches. All items coming into contact with the patch during application and removal from the subject and storage for analytical retention are analyzed for drug content.

- After application of the patch to the subject, the pouch, release liner and all items coming into contact with the patch are retained for analysis.
- The worn patch is retained for drug content analysis.
- Upon removal of the product after prescribed wear period, the skin (at site of application) is swabbed and the swab is retained for drug content analysis.

Study Objectives

The objectives of these studies are: 1) to determine the absolute bioavailability of scopolamine patch, 2) to determine the residual drug content in worn patches, and 3) determine absorption rates from patches based on residual drug content and derived PK parameters.

Study Outcome Measures

The outcomes of this study are to determine pharmacokinetic parameters of scopolamine in healthy adult subjects. The primary outcome measure of the study is to determine the maximum serum concentration of scopolamine (C_{max}). The secondary outcome measures include clearance (Cl), volume of distribution (V), elimination rate constant (K_{el}), time of maximum serum concentration (T_{max}) of scopolamine, and area under the serum concentration-time curve (AUC). In addition, we will determine residual drug content from worn Transderm Scōp® patches to estimate total amount of absorbed scopolamine.

Pharmacokinetic and statistical considerations

Pharmacokinetics (PK) Analyses

Scopolamine concentrations will be measured in serum samples collected from each subject. Actual sampling times will be used to estimate PK parameters. Non compartmental and compartmental analyses will be conducted to estimate the primary PK parameters such as clearance (Cl), volume of distribution (V), elimination rate constant (K_{el}), maximum serum concentration (C_{max}); time of maximum serum concentration (T_{max}) and area under the serum concentration-time curve (AUC). Absolute bioavailability will be calculated as follows:

$$Absolute\ bioavailability = \frac{AUC_{patch}/Dose_{patch}}{AUC_{IV}/Dose_{IV}}$$

Equation 1: For determination of the absolute bioavailability for the Transderm Scōp® patch. The patch refers to the Transderm Scōp® transdermal system.

Statistical Analysis Plan

Descriptive statistics for drug content (i.e., arithmetic mean, median, standard deviation, minimum amount, maximum amount, coefficient of variation) will be calculated. In addition, mass balance will be calculated. Drug content in the unworn patch will be analyzed, the mean amount will be calculated and will be used to estimate amount of drug absorbed after wearing the transdermal system. Unworn systems will all be from the same lot (as printed on the patch pouch), and a minimum of 10 unworn systems will be analyzed for drug content. Drug absorption will be determined by subtracting the residual drug content from the initial drug amount as mentioned on the product label.

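### Does the crossover need a stated treatment order, and a planned summary of absolute bioavailability, before its first objective can be met?

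*Combined protocol and SAP*

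**What the plan says.** Description of Study Design gives a "two arm, open-label, crossover, two treatment sessions study (n=24 healthy adult subjects) with one week washout period between each study session" and adds "Each subject will be his/her own control". Study enrollment provides for "ten alternates who could replace subjects who drop out from the study for any unforeseen reason" and says "Enrollment will continue until 24 complete the study". On order, Study schedule offers only this: "For the treatments, either the patch will be applied behind the ear or the drug will be intravenously administered". No section mentions randomisation, sequence groups, a fixed order, or the order an alternate receives.

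Study Objectives lists first "1) to determine the absolute bioavailability of scopolamine patch". Study Outcome Measures names Cmax as primary and puts AUC among the secondary measures; absolute bioavailability is not listed there. Under Pharmacokinetics (PK) Analyses, "Absolute bioavailability will be calculated as follows" introduces Equation 1, the ratio of dose-normalised patch AUC to dose-normalised intravenous AUC. The Statistical Analysis Plan then says "Descriptive statistics for drug content (i.e., arithmetic mean, median, standard deviation, minimum amount, maximum amount, coefficient of variation) will be calculated", and gives no corresponding list for F.

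**The concern.** Objective 1 is a comparison within each subject of two sessions held at different times. If everyone received the treatments in the same order, route and period would be a single contrast. Any session-to-session shift in AUC would enter F, and no later analysis could take it out. The text does not exclude that arrangement, nor an unbalanced mix of orders. With ten alternates and no rule on their order, even a balanced start could drift.

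The statistical section deepens the doubt. It lists a mean, median, standard deviation, range and coefficient of variation for drug content, yet for the quantity named in objective 1 it gives only a formula. It does not say whether F is computed per subject or from means, or what interval goes with it. The patch dose in Equation 1 is not defined either. It could be the labelled 1.5 mg or the absorbed amount derived from residual drug.

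**Working it through.** **Inputs.** From the documents: 24 completers, ten alternates, two sessions, labelled patch content 1.5 mg, intravenous dose 0.4 mg. The documents give no alpha, power, CV or precision target behind the 24, so that figure cannot be reproduced. Assumed for illustration: within-subject CV of AUC (CVw) 30%, between-subject CV of true F (CVF) 0 or 30%, and period effects of 2%, 5% and 10%.

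**1. Precision with 12 subjects per order.** The variance of one subject's log F is 2·ln(1+CVw²) + ln(1+CVF²).
- CVF 0: 2 × 0.0862 = 0.1724; SE = √(0.1724/24) = 0.0847. With t(22) = 2.074 the 95% limits are exp(±0.176) = 0.839 to 1.192 times F.
- CVF 30%: 0.1724 + 0.0862 = 0.2586; SE = 0.1038; limits 0.806 to 1.240.

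**2. One order for all 24.** F is off by the whole period effect p. Coverage of the nominal 95% interval comes from the noncentral t with 23 df and noncentrality ln(1+p)/SE.

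| p | Noncentrality (CVF 0) | Coverage, CVF 0 | Coverage, CVF 30% |
|---|---|---|---|
| 2% | 0.0198/0.0847 = 0.23 | 0.944 | 0.946 |
| 5% | 0.0488/0.0847 = 0.58 | 0.914 | 0.926 |
| 10% | 0.0953/0.0847 = 1.13 | 0.810 | 0.858 |

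Over CVw 20% to 40% with CVF 30%, coverage is 0.913 to 0.934 at p = 5% and 0.803 to 0.888 at p = 10%. The least favourable case is CVw 20% with CVF 0: 0.870 at 5% and 0.641 at 10%.

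**3. Two orders, unequal (n1:n2).** Without a period term, the bias on the log scale is the period effect times (n1−n2)/24. With a period term the bias is zero, and the variance relative to 12:12 is 24²/(4·n1·n2).

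| Split | Bias left from a 10% effect, no period term | Variance ratio with period term | 95% limits with period term (CVw 30%, CVF 0) |
|---|---|---|---|
| 12:12 | 0 | 1 | 0.839–1.192 |
| 16:8 | 1.10^(1/3) − 1 = 3.2% | 576/512 = 1.125 | 0.830–1.205 |
| 18:6 | 1.10^(1/2) − 1 = 4.9% | 576/432 = 1.333 | 0.816–1.225 |

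**4. How far alternates could unbalance the orders.** Moving from 12:12 to 16:8 with four replacements needs all four dropouts in one order and all four replacements in the other. If dropout is unrelated to order and replacements are allocated by coin toss (both assumed), the chance is 2·C(12,4)/C(24,4) × (1/2)⁴ = 990/10,626 × 0.0625 = 0.0058, about 0.6%. If instead the order of all 24 were tossed without restriction, a split of 16:8 or worse would have probability 15.2%. Step 3 gives the cost in either case.

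**5. Can the analyst recover what is unwritten?** Parameters are estimated from actual sampling times (Pharmacokinetics (PK) Analyses), so each subject's session order is known. A period term can be fitted afterwards whenever both orders occur. Every subject contributes both AUCs, so per-subject F, its geometric mean and an interval need no new data.

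**6. Patch dose.** If a share r of the labelled 1.5 mg is absorbed, the two readings of Equation 1 differ by 1.5/(1.5·r) = 1/r: 2.0 at r = 0.5 and 1.25 at r = 0.8 (r assumed). Study products lists 1.5 mg for the patch beside 0.4 mg for the intravenous product. The Statistical Analysis Plan treats the residual-drug result as absorption and never calls it a dose. The labelled content is therefore the natural entry.

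**The case for a change.** The strongest case for a change is that order cannot be repaired after dosing. A summary of F can be added at any time, but a single order, once given, cannot be undone. The sample taken an hour before each dose would reveal carried-over drug, but not other differences between sessions. The remedy is cheap: a sequence list and a sentence on alternates, with no extra subjects or samples. The patch-dose ambiguity also needs no assumed nuisance effect to matter.

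Much of this is true. The omissions are real, and a single order would confound route with period. But the damage depends on two things the documents do not indicate. The first is a single order, the less natural reading of a two-arm crossover. The second is a sizeable period effect. The obvious sources of one are limited by the one-week washout, healthy subjects, restrictions on medication and recent alcohol, and a measured serum concentration as endpoint. With two orders, imbalance costs only a little precision. For a trial already allocating two orders, the remedy would only record existing practice.

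Nominal coverage also drives no decision here. The study tests no hypothesis and sets no acceptance limit. On the patch dose, both versions of F can be calculated from the same results, and the listed products point to one of them.

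**Conclusion.** No change to the plan follows. The protocol leaves three details unwritten: the allocation of order (including for alternates), the across-subject summary of F, and the definition of the patch dose. None is a stated rule that produces a wrong answer. On the natural reading, with two orders, a period term removes any bias, and at CVw 30% even an 18:6 split moves the 95% interval only from 0.84–1.19 to 0.82–1.22 times F. Coverage falls to 81–86% only with one order for everyone and a period effect of about 10%; at 2% the loss is about half a percentage point. The summary of F and the choice of denominator are gaps that an analyst fills sensibly from data already planned.

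This rests on assumed CVs and period effects, since the documents give none, and on reading the design as two orders. If it emerged that all 24 had taken the same order, F would have to be reported as a comparison in which route and period cannot be separated.

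### Absorbed drug is defined only as initial minus residual, so unassayed loss counts as absorption, and no comparison with the amount implied by the IV session is planned

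*Combined protocol and SAP*

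**What the plan says.** The Statistical Analysis Plan announces a balance, "In addition, mass balance will be calculated", without terms, denominator or acceptance range. Its rule for absorbed drug comes at the end of the same paragraph: "Drug absorption will be determined by subtracting the residual drug content from the initial drug amount as mentioned on the product label". Earlier in that paragraph a different starting amount appears. Unworn systems from one lot are assayed, "a minimum of 10 unworn systems will be analyzed for drug content", and "the mean amount will be calculated and will be used to estimate amount of drug absorbed after wearing the transdermal system". The plan therefore names two initial amounts, the assayed mean and the label content.

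Under Residual drug analysis determination of strength, the worn patch, the pouch, the release liner, other contact items and a post-removal skin swab are all assayed. The text does not say whether the residual to be subtracted includes the items other than the worn patch. Study Outcome Measures gives the residual content the role of estimating total absorbed drug.

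Every subject receives both routes: "Each subject will be his/her own control". Equation 1 defines absolute bioavailability from the AUC and dose of each session. The third objective is to "determine absorption rates from patches based on residual drug content and derived PK parameters", so it names both sources together. Neither the Statistical Analysis Plan nor the PK section says how they are to be compared or combined.

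**The concern.** Subtraction measures what is no longer in the patch. It equals the amount absorbed only if nothing was lost on the way and the assay recovers everything that stayed behind. Incomplete extraction of the worn patch, breakdown of drug and drug still in the skin after swabbing all make the residual look smaller, and so make absorption look larger. The rule has no term that could show this.

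A mass balance would normally be where such a shortfall appears. If its absorbed term is the same subtraction, it cannot show one. The study could check the depletion figure against a quantity that does not use the patch assay, because the IV session calibrates each subject's AUC in milligrams. Without a stated comparison, a gap between drug that left the patch and drug that reached the circulation could be reported as absorption. That would affect the estimate of total absorbed drug and the absorption rates of the third objective.

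**Working it through.** The documents give no mass-balance figure to reproduce, so the check is algebraic, followed by an illustration.

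**From the documents:** label content L = 1.5 mg and IV dose 0.4 mg (Study products); absorption by subtraction, and two initial amounts (Statistical Analysis Plan).

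**Assumed, not in the documents:** systemic amount A = 0.70 mg; drug on assayed swab, pouch, liner and contact items S = 0.05 mg; unassayed loss X = 0, 0.10 or 0.30 mg; true and assayed mean content U = 1.50 mg, varied by ±10%.

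The measured worn-patch residual is R = U − A − X − S.

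**1. What the rule reports as absorbed.** L − R − S = A + X + (L − U). If only the worn patch is subtracted, it is L − R = A + X + S + (L − U). Unassayed loss enters in full either way. Using the label amount adds L − U: +0.15 mg at U = 1.35 and −0.15 mg at U = 1.65.

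**2. What a balance can show, under four readings of the undefined formula.**

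- Same initial amount throughout: (U − R − S + R + S)/U = 100% for any X.
- Label in the subtraction, assayed mean as denominator: L/U for any X. This is 111.1% at U = 1.35, 100% at 1.50 and 90.9% at 1.65, and shows only label against assay.
- Worn patch alone subtracted, other items then added, over label: 1 + S/L = 1.55/1.50 = 103.3% for any X.
- Recovery only, with no absorbed term: (R + S)/U = 1 − (A + X)/U. This moves, but A and X are inseparable.

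**3. Illustration at U = L = 1.50 mg.**

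| X (mg) | R (mg) | Apparent absorbed, 1.50 − R − S (mg) | Balance by subtraction | Recovery only | Balance with systemic amount, (A + R + S)/U |
|---|---|---|---|---|---|
| 0 | 0.75 | 0.70 | 100% | 53.3% | 100% |
| 0.10 | 0.65 | 0.80 | 100% | 46.7% | 93.3% |
| 0.30 | 0.45 | 1.00 | 100% | 33.3% | 80.0% |

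Released minus systemic is 0, 0.10 and 0.30 mg, or 0%, 6.7% and 20.0% of initial content.

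**4. The systemic amount is already within reach.** Equation 1 times Dose_patch gives Dose_IV × AUC_patch / AUC_IV, because Dose_patch cancels. With 0.4 mg IV, AUC ratios of 1, 2 and 3 give 0.4, 0.8 and 1.2 mg. The assumed 0.70 mg corresponds to a ratio of 0.70/0.4 = 1.75.

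**5. Dose basis.** Study products names the IV drug as the hydrobromide and the patch content as scopolamine. If 0.4 mg is salt, the uncorrected formula gives the systemic amount as salt while the patch is in base. The documents give no conversion, so take a base fraction of 0.7 to 1.0 as an assumed range. A systemic figure of 0.70 mg then becomes 0.49 to 0.70 mg. At R = 0.75 and S = 0.05 the balance is (0.49 + 0.80)/1.50 = 86.0% at one end and (0.70 + 0.80)/1.50 = 100% at the other. The basis alone can move it by 14 percentage points.

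**The case against.** A reader might infer that the planned balance closes by construction and cannot fail. The text does not say so. The balance is undefined, nothing states that the subtraction enters it, and a recovery-only balance fits the wording equally well and does not close. With two initial amounts, even a subtraction-based balance need not be 100%. Nor must adding the swab and liner push it above 100%: with subtraction from label and an assayed mean of 1.65 mg (assumed) as denominator, it is (1.50 + 0.05)/1.65 = 93.9%.

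A second tempting reading is that the plan cannot detect lost drug at all. That is too broad, since drug on the pouch, liner, contact items and swab is measured directly. Only unassayed loss is invisible.

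Nor is the balance the only possible check. Equation 1 carries the PK amount, and a careful reader of the results could see the gap. At X = 0.10 in the illustration, bioavailability against label content is 0.70/1.50 = 46.7%, beside a depletion of 0.80/1.50 = 53.3%. The information will exist; what is missing is a planned comparison.

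Finally, a PK-based balance can itself suggest loss where there is none. Unmatched dose basis, different clearance in the two sessions, or unequal AUC coverage (sampling to 120 h after the patch and 48 h after IV) would all appear as unaccounted-for drug.

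All of this stands. It limits the claim and shapes the fix. It does not change the fact that the stated absorption rule counts unassayed loss as absorbed, or that no comparison is specified.

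**Conclusion.** The point holds in limited form. The plan's one calculation rule for absorbed drug overstates absorption by the whole unassayed loss, and also by the swab, pouch and liner drug if these are not subtracted. No balance resting on that rule can reveal the unassayed part. In the illustration, a loss of 0.30 mg raises apparent absorption from 0.70 to 1.00 mg, or 43% (0.30/0.70), with the balance unchanged. The true size is unknown, because the documents give no recovery or systemic figures; the algebra does not depend on the assumed values.

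The documents do not support the conclusion that the mass balance is bound to close, or that the PK evidence is ignored. The defect is an undefined balance, a depletion figure called absorption, and no planned comparison with the systemic amount. It bears on the estimate of total absorbed drug and on the third objective. The primary outcome, Cmax, and the AUCs are unaffected.

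**What to change.** Amend the Statistical Analysis Plan as follows.

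1. Use one initial amount, the assayed mean of the same-lot unworn patches, in both the subtraction and the balance, and write out the balance with its terms and denominator.
2. Compute initial minus worn patch minus swab, pouch, liner and contact items, and label it 'released', not 'absorbed'.
3. For each subject compute systemic amount = Dose_IV × AUC_patch / AUC_IV, with AUCs extrapolated to infinity. State the IV dose and patch content on the same basis, both as scopolamine base or both as salt.
4. Report the paired difference, released minus systemic, as a mean with confidence interval, and the percentage of initial content unaccounted for.

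The cost is SAP wording and a few derived variables from data already planned. The difference will carry within-subject AUC variability and assumes equal clearance in the two sessions, so a shortfall should be read as unaccounted-for drug, not as proven loss. Error in the mean unworn content is common to all subjects and is not captured by an interval across the 24 differences, so its standard error should be reported alongside.

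### The SAP gives two different starting amounts for drug absorbed, the assayed mean of unworn patches and the label amount, and does not say which governs

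*Combined protocol and SAP*

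**What the plan says.** The Statistical Analysis Plan section gives two rules for the same quantity.

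- Assayed rule: drug content is measured in unworn patches, and "the mean amount will be calculated and will be used to estimate amount of drug absorbed after wearing the transdermal system". On numbers, "a minimum of 10 unworn systems will be analyzed for drug content". The lot condition reads "Unworn systems will all be from the same lot (as printed on the patch pouch"; its subject is the unworn systems only.
- Label rule, which closes the section: "Drug absorption will be determined by subtracting the residual drug content from the initial drug amount as mentioned on the product label".

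Study products describes a "patch containing scopolamine (1.5 mg) to be worn for 3 days (72 hr" period. The section also says "In addition, mass balance will be calculated" but does not name the starting amount for it.

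Under Study Outcome Measures, residual content is measured in worn "patches to estimate total amount of absorbed scopolamine". Objective 3 under Study Objectives seeks absorption rates from residual content together with PK parameters. The residual drug analysis section adds that drug is assayed in more than the patch: "All items coming into contact with the patch during application and removal from the subject", with a skin swab taken after removal.

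**The concern.** Both sentences define drug absorbed, and only one can be the estimator. No text makes one primary and the other a sensitivity analysis, or reserves the assayed mean for mass balance. If the closing sentence governs, the unworn assays lose the purpose that the plan gives them, and any departure of the lot from its label amount passes in full into every subject's absorbed amount. The spread between subjects would not reveal this, because the same constant is added to everyone. If neither sentence governs, the plan yields two point estimates from one data set, and the choice between them could be made after the assays are seen.

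**Working it through.** The plan states no absorbed amount, so there is no figure of its own to reproduce.

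**Inputs from the documents.** L = 1.5 mg (Study products; the label itself is not reproduced, so equating the two is a small inference). Unworn patches: at least 10. Completing subjects: 24.

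**Inputs assumed.** Lot mean M, patch-to-patch CV (2% or 5%), amount absorbed (0.5 to 1.0 mg) and assay recovery. The documents give none of these.

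**Step 1. Gap between the rules on the same data.** For subject i with residual R_i and assayed unworn mean X:

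(L − R_i) − (X − R_i) = L − X = 1.5 mg − X

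R_i cancels and the number of subjects does not enter. The mean, median, minimum and maximum absorbed all move by this constant. The SD does not move; the coefficient of variation does, because its denominator changes.

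**Step 2. Possible size of the departure, L − M.**

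| Departure of lot mean from label | Shift | Share of 1.0 mg absorbed | Share of 0.5 mg absorbed |
|---|---|---|---|
| 2% | 1.5 × 0.02 = 0.03 mg | 3% | 6% |
| 5% | 1.5 × 0.05 = 0.075 mg | 7.5% | 15% |

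If the lot mean is exactly 1.5 mg, the gap is zero in expectation only. X still varies around M with standard error 1.5 × CV/√10, which is 0.0095 mg at 2% CV and 0.0237 mg at 5% CV.

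**Step 3. Which rule is closer to the truth, with one shared lot and complete recovery.** Let s = 1.5 × CV. The root mean squared error (RMSE) of the 24-subject mean is:

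- label rule: √[(L − M)² + s²/24]
- assayed rule: s × √(1/10 + 1/24)

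| Departure | CV | Label rule | Assayed rule |
|---|---|---|---|
| 5% | 2% | 0.075 mg | 0.011 mg |
| 5% | 5% | 0.077 mg | 0.028 mg |
| 0% | 2% | 0.006 mg | 0.011 mg |
| 0% | 5% | 0.015 mg | 0.028 mg |

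The two are equal when |L − M| = s/√10, which is 0.63% of label at 2% CV and 1.58% at 5% CV. Beyond that the assayed rule is the more accurate.

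**Step 4. Where those conditions fail.**

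- Different lots, for example unworn at 1.53 mg and worn at 1.47 mg: assayed bias = 1.53 − 1.47 = +0.06 mg; label bias = 1.50 − 1.47 = +0.03 mg. The ranking reverses.
- Recovery r = 0.95 and absorbed amount A = 0.5 mg: assayed bias = −(1 − r)A = −0.025 mg whatever the lot mean. Label bias = (L − M) + (1 − r)(M − A), which is +0.050 mg at M = 1.5, −0.021 mg at M = 1.575 and +0.121 mg at M = 1.425.

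**The case against.** The strongest reply is that the documents show only an inconsistency, not that the label rule is the worse one. Its size is simply 1.5 mg minus an unknown number. The assayed rule is better only with a shared lot and a lot mean away from label, and the plan fixes the lot only for the unworn systems. The label rule does better with the different lots of step 4, with a lot mean at label, and marginally at 95% recovery with 5% overfill. The analysis is descriptive, so reporting both values would expose any selective choice. All of this stands. It limits the claim about accuracy and makes the fix conditional on lot; it does not remove the need to name one rule.

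A reader might also infer that residual drug content is undefined. The documents do not support that: objective 2 and the outcome measures tie the term to worn patches. What stays open is narrower, namely how the swab, release liner, pouch and other contact items enter drug absorbed and mass balance.

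**Conclusion.** The contradiction is in the current text and should be fixed before the patch assays are analysed. The gap of 1.5 mg minus the assayed mean is exact. Its size and sign cannot be known from the documents; the 0.03 to 0.075 mg, or 3% to 15% of the amount absorbed, rests on an assumed 2% to 5% departure and an assumed 0.5 to 1.0 mg absorbed.

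The reach is limited to the residual-based total absorbed and the residual-based part of objective 3. A reader might infer that the primary outcome or the absolute bioavailability is compromised. The documents do not support this. Cmax and AUC come from serum concentrations, residual content (objective 2) needs no starting amount, and no hypothesis test depends on the choice. Equation 1 would be affected only if its patch dose were derived from residual content, and the plan does not define that dose.

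Confidence is high that the two sentences conflict. The preference for the assayed rule depends on worn and unworn patches sharing a lot, and the figures in step 3 also on complete recovery.

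**What to change.** In the closing sentence of the Statistical Analysis Plan, delete the words that tie the initial amount to the label. Then state:

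1. Amount absorbed = mean assayed content of unworn systems from the same lot as the worn patch (at least 10, same assay as the worn patches) minus the drug recovered from the worn patch.
2. How drug found on the swab, release liner, pouch and other contact items enters drug absorbed and mass balance, with the same starting amount used for mass balance.
3. If a worn patch comes from a lot with no assayed unworn systems, the label amount is used for that patch and flagged.
4. Otherwise the label-based value is reported only as a sensitivity figure.

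The unworn assays are already planned, so the change is mainly wording. Two costs remain. Keeping to one lot is a supply condition: it must cover 24 completers, any of the ten alternates who are used, and at least 10 unworn patches. In addition, the sampling error of the 10-patch mean is shared by all subjects and is not averaged away: about 0.009 mg at an assumed 2% CV and 0.024 mg at 5%. If the lot mean is at or very near label, the label rule would have been slightly more precise.
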